**NCT02188121**

Protocol Title: Clinical trial to reduce cardiovascular health risks in  
patients with serious mental illness

Statistical Analysis Plan Date: 02/10/2018

Background: This trial focuses on SMI patients who are potentially eligible for cardiovascular prevention therapy (through statin and angiotensin medications such as angiotensin receptor blockers or ARBs) but who have not yet received it. The trial compares a prevention strategy intervention with usual care with respect to use of therapy. The trial includes those on partial therapy and excludes those with detected cardiovascular disease or diabetes, and assesses whether the intervention increases cardiovascular prevention use relative to usual care.

Eligibility summary: Eligibility criteria include a diagnosis of schizophrenia, schizoaffective disorder, or bipolar disorder; second generation antipsychotic (2GA) therapy within the past six months before trial entry; and mental health care at one of the study sites at the time of trial entry. We exclude subjects who already have a diagnosis of diabetes or cardiovascular disease; who already are receiving therapy with both statins and angiotensin medications (i.e., the same therapeutic drug classes as used in the intervention); or who have contraindications to both drug classes.

Primary study outcome: The main outcome is use of the cardiovascular prevention medications over the 12-months after study initiation. For each individual, we define the primary outcome as the proportion of the 12 follow-up months during which she/he either received any of the prescribed medication or the medication became clinically contraindicated after trial entry (as decided by the treating physician). We will assess the outcome using medication counts at each study visit (i.e., at the 3-, 6-, 9-, and 12-month study visit), supplemented by subject self-reports and the clinic chart review. For subjects who are eligible to receive both statins and ARB medications at baseline, we will calculate the number of days that they receive both medications during the 12 months of follow-up. For subjects who are eligible to receive only one of the two medications at baseline (i.e., because of pre-existing therapy with or because of contraindications to the other prevention medication before trial entry), we will calculate the number of days that they receive the medication during the 12 months of follow-up, with the same approach for addressing changes in subsequent eligibility.

Analysis of the primary study outcome: The primary analysis will follow the intention-to-treat (ITT) principle. We will use regression analysis to estimate the mean average of the primary outcome in each group and the difference between the mean outcomes, along with its 95% confidence interval and using the p-value for a null hypothesis. If clinically meaningful imbalances are detected in baseline covariates despite randomization, we will adjust for those covariates. If necessary, we will adjust for selection bias due to loss to follow-up via inverse-probability weighting. In supplemental analyses to the main ITT approach, we also will conduct appropriately adjusted per-protocol analyses. We will use STATA 13.0 for all analyses. We also will examine a number of pre-specified subgroup analyses, in which we examine whether the intervention might be more effective among those SMI patients who are more likely to receive fragmented care or less likely to be adherent to complex treatment regimens, e.g., SMI patients with Medicaid versus those with commercial health insurance.

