Study nurse prescribes fixed dose statin and/or ARB drugs (Intervention arm only). If subjects are randomized into the treatment arm and are already taking either a statin or any anti-hypertensive medication, they will be prescribed only the drug they are not already taking (e.g. participants on a statin will be prescribed only losartan). If subjects are already taking either a statin or anti-hypertensive medication, we will not alter the dosage of the previously prescribed medication.

We will send letters about the trial to the subject's PCP, regardless of subject's randomization.

Intervention arm subjects will get an additional blood draw in-between the medication visit and first follow-up visit to ensure it is safe for them to continue taking the study medications.

Step 4: Follow-up Visits (every 3 months for 12 months)

RAs conduct follow-up interviews, perform pill counts, and collect urine pregnancy tests (all arms)

Study nurses collect blood samples and vital signs; conduct safety checks; track visits (dates, clinician type), diagnoses, prescription drugs (names, doses, pill counts of cardiovascular drugs), and medical events (all arms)

Study nurses will record and reconcile medication lists at every visit, and note changes in medications.

Study nurse prescribes additional fixed dose statin and/or ARB drugs (Intervention arm only).

Participants who have baseline CK values within 2*ULN will be enrolled in the study. If these participants are randomized into the treatment arm, and will be receiving treatment with a statin, they will be asked to come for additional safety blood draws once per month in addition to one draw one week following the first dose of study drugs. This draws will be done to ensure participant safety while taking the study medications. If a trend of increasing CK is observed, the study medications will be discontinued (Intervention arm only).

Participants prescribed the ARB who exhibit symptoms of hypotension (e.g., syncope, dizziness) and/or have an SBP measurement of <100 mmHg at the follow-up visit will additionally be evaluated for orthostatic hypotension and tachycardia. Study PIs will be notified, and will make a decision based on these criteria to either continue or discontinue the ARB at this time. These participants will be asked to come back within one week of their follow-up visit for an additional blood pressure check. (Intervention arm only).

Step 5: Final Assessment

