Outpatient Bipolar Clinic. After running data queries using the study's inclusion and exclusion criteria, we will request detailed data through RPDR in order to directly contact those patients who are eligible for the study and who have consented to be contacted in future for research purposes. Detailed data requests, including identifying information such as medical information and contact information, will be approved by the Partners IRB.

Random (1:1) allocation: We will assess eligibility, NP's will conduct the informed consent process, then randomize eligible subjects to one of two arms: 1) fixed-dose statin and/or ARB; or 2) usual treatment with greater monitoring. In both arms, the patient's clinical care remains within the original mental health clinics. We will use a computerized random number generator. Participants unable to be randomized due to eligibility issues discovered at the first study visit will still be followed as not-randomized subjects.

Randomization scheme: We will start with a concealed, simple subject-level randomization scheme, e.g., web or telephone delivered random sequence. [104-106] We also will consider concealed, block randomization schemes, e.g., accounting for clinic and time with randomly varied block sizes. An investigator not involved in the arm assignment or clinical care of subjects will perform the generation and allocation concealment.

Intervention: The multi-component intervention exploits a number of strategies from incentive theory and behavioral economics, including: a) a simplified drug regimen; b) free treatments; c); framing of goals and goal setting; and d) focus on immediate cardiovascular risks within a larger plan for risk reduction.^[107-114]

Control: We will compare the initial treatment intervention with usual treatment (control arm), with both arms superimposed on a system of regular monitoring base. The RA/APRN pair will make no effort to alter or influence treatment or use of that treatment for subjects in the control arm. Note that our goal in the Control arm is to characterize "usual treatment". We will not intervene in this care except in emergencies requiring us to notify the patient's treatment team. Some patients who need care for metabolic syndrome may not be receiving it – just as they would if not in our trial.

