Follow-up: Up to 24 months. We will censor subjects (from the intervention) who receive a diagnosis of diabetes, when they develop a cardiovascular or cerebrovascular event, who die, or who leave the study health care systems. During each follow-up visit, the study nurse will review all prescription drugs and the RA will perform pill counts of cardiovascular drugs (we will ask subjects to bring all of their drugs in to each study visit). The study nurse will perform safety checks comparable to that during baseline evaluation. For subjects in either arm identified during our safety checks or who have events, we will recommend that they receive more intensive care from primary care physicians, cardiologists, or endocrinologists, and will message their clinicians. We will continue to monitor these subjects throughout the follow-up period albeit now on a more intensive treatment regimen.

At the end of the study, we will characterize the clinical care for subjects in both study arms, thus providing a detailed description of "usual treatment," and information about care received from other clinicians for subjects in the intervention arm. We will report on all clinicians seen (specialty, location, visit frequency and timing), conditions diagnosed and treated (psychiatric and medical), and cardiovascular conditions diagnosed and treated (major events such as ED visits or hospitalizations, diagnoses, drugs, doses). We will compile adverse events using the CATIE adverse event reporting tool as a base.^[115]

Subjects will have the option to continue coming to follow-up visits after the 12-month endpoint every 6 months for another 12 months. We will not continue to prescribe medicine to subjects in the intervention arm, rather we would continue to collect data so we can get a longer-term picture of "usual treatment" for those in each study arm (including non-randomized). RAs will perform pill counts at these additional follow-up visits, to get information about medication adherence for an additional year. NPs will continue to draw blood and ask subjects about their medications and medical history. Participants who have already signed consent and would like to participate in the post-study year of follow-up visits, will be asked to the new consent form prior to starting study procedures.

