whereby the usual clinical care is enhanced due to awareness of the study aims. Clinicians who are aware that their patients' care is being evaluated on certain criteria may consciously or unconsciously pay more attention to these criteria. This effect typically makes the treatment as usual arm appear more robust and reduces the odds of detecting an intervention effect. Our goal is to avoid this contamination effect while also ensuring that PCPs are adequately informed and have an opportunity to intervene if they deem it necessary. As per our study design, there is no ongoing communication with the PCP. By sending them a letter before study arm assignment, we ensure that the PCP can request the patient be excluded. As the individual responsible for the overall medical care of the participant, the PCP has the power to veto patient participation in this study. The PI's name and contact information on this study will be included in the PCP letter so that the PCP may contact the PI with study design questions. If the PCP desires to know whether the patient is going on the medication arm they then have to go through routine channels (e.g. ask the patient) to obtain this information. If the PCP contacts the research team asking for this information, we will provide it. But this approach minimizes "contamination" from the study team, and approximates routine clinical care if the patient were placed on a medication by another clinician. To further minimize contamination we will not communicate routine lab results to the PCP. However if in the course of the study, should lab results require immediate attention, study nurses will triage and contact subject PCP accordingly.

We will send another letter at study completion informing the participant's PCP of the treatment the participant received as a part of their study.

Anytime staff attempts to contact a participant's PCP or any other provider, staff will confirm the contact information with the participant prior to attempting communication. This will be done to ensure that the participant still receives care from the indicated provider, as participants occasionally change clinics over the course of the study period.

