The study staff will request that participants agree to have All Payers Claim Database (APCD) queried by study staff such that they may access all insurance claims made on behalf of the participant. The APCD is an excellent source of ancillary information to reconcile all patient report and medical record information. Participants will not be required to agree to have the APCD accessed in order to participate. There is a detailed data management plan that details how all data will be kept and how participant information with remain private. For secure data transmissions, we use a secure FTP, which is available through Partners Research Computing (RC). We then keep the data on our dedicated servers managed by RC, which are behind the Partners firewall. We limit data access such that only the programmer/analysts working on the project can access the data; the data remain on the servers at all time; and at no time, do any of the data leave the servers (e.g., no data on laptops, desktops, or other devices).

Blood Pressure Checks: Participants prescribed the ARB who exhibit symptoms of hypotension (e.g., syncope, dizziness) and/or have an SBP measurement of <100 mmHg at the follow-up visit will additionally be evaluated for orthostatic hypotension and

tachycardia. These participants will be asked to come back within one week for an additional blood pressure check and study PIs will be notified.

Subjects who exhibit a combination of any 2 of the 3 criteria (self-reported/observed symptoms, SBP <100 mmHg, or abnormal orthostatic measures) or all 3 criteria will be discontinued from the ARB for at least one week before coming back in for the additional safety follow-up. Study nurses will assess whether the signs/symptoms are still present, or have been alleviated after discontinuing the study drug. Study PIs will be contacted to make the decision to continue/discontinue the study drug.

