Characterization of Usual Treatment: We also will carefully describe care under Usual Treatment, including the timing of initiation, treatment choice, adherence, prescribing clinicians, and visit patterns for subjects in the control arm. We will characterize the involvement of other clinicians for subjects in both arms, and clinic traits.

Treatment Operational Definition: To start, we will use the same treatment definition for both study arms, i.e., current use of a statin and angiotensin drug. Because there are multiple potential drugs for cardiovascular prevention, we will alter this definition in a series of sensitivity analyses. For example, we will examine a minimal cardiovascular treatment variable in which we define treatment as current use of any cardiovascular drug, independent of the therapeutic class or mechanism of action. We also will examine a partial treatment variable in which we count the number of distinct cardiovascular prevention drugs.

Analysis approach 1: We will plot the percent on "adequate" CVD prevention care, at baseline and the four quarterly follow up times to monitor how treatment activity unfolds over time in the two arms of the trial. At any given follow-up point we will be comparing

two binary outcomes (on or off treatment) and will use standard methods for comparing two proportions to test statistical significance and get confidence intervals for the difference in the percent on treatment in the two arms. We will use a Bonferroni correction so the four separate tests or CIs will have an overall level of 0.05 or 95% CI, respectively.

Analysis approach 2: We will use all available follow-up data to construct a summary measure of the mean percentage of follow-up time during which each group was on treatment. Since we expect the distribution of outcomes to be non-normally distributed, we will get a test of significance for no difference between the mean outcomes in the two arms using a randomization test. A 95% confidence interval for the difference of percentage of time on Tx will be obtained using bootstrap methods. We will use STATA 13.0 for all analyses.

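### The SAP's primary outcome counts time after a post-entry contraindication as drug use, a credit likely to fall more in the intervention arm, and no version without it is planned

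*SAP*

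**What the plan says.** The SAP (Background) says the trial assesses whether the intervention increases use of prevention medication relative to usual care. Under Primary study outcome, each person's score is the proportion of the 12 follow-up months in which they "either received any of the prescribed medication or the medication became clinically contraindicated after trial entry (as decided by the treating physician". The same handling of later ineligibility carries over to the day counts that follow.

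The protocol gives intervention participants safety procedures that controls do not have:

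- Table 1, Step 3: "Intervention arm subjects will get an additional blood draw in-between the medication visit and first follow-up visit".
- Table 1, Step 4: statin recipients under the CK rule have a draw one week after the first dose and then monthly. "If a trend of increasing CK is observed, the study medications will be discontinued (Intervention arm only".
- Table 1, Step 4 and section V, Blood Pressure Checks: participants prescribed the ARB who show signs of hypotension are assessed against three criteria. Meeting two stops the drug for at least a week. "Study PIs will be contacted to make the decision to continue/discontinue the study drug". Step 4 marks this as applying to the intervention arm only.

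For controls, section IV (Control) says "The RA/APRN pair will make no effort to alter or influence treatment or use of that treatment for subjects in the control arm". Section V (Contacting patient's current treater) adds that "we will not communicate routine lab results to the PCP", although results needing immediate attention are passed on. Quarterly bloods, vital signs and safety checks run in all arms, and section IV (Follow-up) states: "For subjects in either arm identified during our safety checks or who have events, we will recommend that they receive more intensive care".

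The protocol's own summary of use, in section VI (Aim 1, Analysis approach 2), is to "construct a summary measure of the mean percentage of follow-up time during which each group was on treatment". It contains no contraindication credit.

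**The concern.** A measure of use should rise when people take more medication. This one also rises when people stop for a medical reason. The two arms do not have the same chance of earning that credit. Intervention participants start on drug by design and most controls do not, so harm caused by a statin or ARB will arise mainly in the intervention arm. The added checks and explicit stopping rules then make it more likely to be found and acted on there. The protocol (Trial Study Design Overview) also offers no second-line drug after a medically significant reaction, so one such stop can fill the remaining months with credited time.

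At stake is what the primary result means. A difference that is partly time on drug and partly time medically excused cannot be read as the extra medication the strategy gets patients to take, which is the question the SAP poses. The SAP has no uncredited version of its primary outcome from which a reader could separate the two parts.

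**Working it through.** The documents give no contraindication rate, so there is no planned figure to reproduce. The check asks how far the credit moves the primary contrast for a given rate.

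**Inputs**

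- Follow-up: 12 months (SAP, Primary study outcome).
- c_int, c_ctl: share of each arm whose drug is judged contraindicated after entry and who are then off it. Not in the documents; assumed.
- m: month of the stop, assumed equal in both arms. Not in the documents; taken as 1, 3 or 6.
- 150 per arm (protocol, Power Calculations), used only in step 3.

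**Step 1: credit within an arm.** A person stopped at month m is credited with 12 − m months not taken. The arm mean therefore rises by c × (12 − m)/12.

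**Step 2: effect on the contrast.** The excess of the credited difference over the difference in actual use is

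(c_int − c_ctl) × (12 − m)/12.

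| Net excess, c_int − c_ctl | m = 1 | m = 3 | m = 6 |
|---|---|---|---|
| 1% | 0.92 | 0.75 | 0.50 |
| 2% | 1.83 | 1.50 | 1.00 |
| 5% | 4.58 | 3.75 | 2.50 |
| 10% | 9.17 | 7.50 | 5.00 |

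Entries are percentage points. For example, 10% against 2% stopped at month 3 gives 0.08 × 9/12 = 6.0 points. Equal rates give 0.

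**Step 3: what this could do to the test.** Suppose actual use were equal in the two arms and the SD of the individual proportion were 0.35 to 0.45 (assumed). The standard error is SD × √(2/150), or 0.040 to 0.052. A 4.6-point credit is then 1.13 to 0.88 standard errors, and a two-sided 5% test would reject about 21% to 14% of the time. A 9.2-point credit gives about 62% to 42%. This is a limiting case: the intervention arm starts on drug, so a real difference in use is expected and the main effect is on the estimate.

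**Step 4: why c_int is likely to exceed c_ctl.**

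| Source of a contraindication judgment | Intervention | Control |
|---|---|---|
| Exposure to statin or ARB | By design, from the start | Only if usual care prescribes (protocol assumes under 15%) |
| Quarterly bloods, vital signs, safety checks | Yes | Yes |
| Early extra safety draw | Yes | No |
| CK draws and CK stopping rule | Statin recipients under the rule | No |
| ARB hypotension rule | ARB recipients | No |
| Usual-care clinicians, clinic chart | Yes | Yes |

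No row favours the control arm. That gives the direction; the size depends on rates the documents do not supply.

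**The case against.** The strongest reply is that the rule itself is even-handed. A control whose physician stops losartan as contraindicated earns the credit, and an intervention participant who simply quits does not. Controls have quarterly checks and chart review too, and reasons unrelated to study drug, such as pregnancy, lithium or raised creatinine, can arise in either arm. The protocol expects adverse effects at these doses to be rare and mild. Treating a medically proper stop as something other than failure is also a legitimate choice for a care-delivery trial. All of this stands. It limits the bias to the difference in rates and leaves the choice of primary outcome to the investigators, but it does not make the rates equal or the credited time medication taken.

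The protocol's Aim 1 measures carry no credit, and nothing says they are withdrawn. That also stands, but the SAP does not tie them to its primary outcome or say which supports a claim about use.

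Several stronger readings are tempting and are not supported:

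- That study investigators who know the arm decide the credit. The SAP names the treating physician. The study PIs decide whether study drug continues, and the documents do not say whether their stop alone earns credit.
- That controls cannot be credited. The wording does not exclude them.
- That every hypotension stop is credited to month 12. Those stops are provisional and reassessed. The SAP also mixes receipt of any prescribed medication with days on both, so the scoring when one of two drugs is stopped is unclear.
- That a medically stopped intervention participant can be set against a control who quits. Those are different events.
- That the excess can be expressed as a share of the differences in the power section. Those are percentages on treatment at one time point, a different measure.

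**Conclusion.** The concern holds in direction and structure. The SAP's primary outcome is labelled use but includes time not on drug, and exposure and the added safety procedures make that time likely to be greater in the intervention arm. The reported difference would then exceed the difference in medication taken.

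The size is unknown. It is about 0.9, 0.75 or 0.5 points per 1% net excess stopped at month 1, 3 or 6. A net excess of 2% to 10% would give 1.0 to 9.2 points, and equal rates would give none. These figures assume that stops are lasting, are credited for the rest of the year, and occur at the same time in both arms. Shorter stops would shrink them. The point does not show that the credited outcome is wrong as a measure of appropriate care, only that it cannot alone support a statement about use.

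**What to change.** In the SAP, pre-specify a second analysis of the primary question: the same intention-to-treat regression contrast, with the outcome defined as days actually on the eligible drug or drugs divided by follow-up days, and contraindicated days counted as off treatment in both arms. This matches protocol Aim 1, Analysis approach 2. Report it beside the credited version, base any statement that the intervention increased use on it, and tabulate the people and months credited in each arm.

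The cost is SAP wording. Pill counts, self-report and chart review are already planned, and the protocol undertakes to settle the analysis before outcome data are examined. The downside is that medically appropriate stops count as non-use in this analysis, so the intervention mean will be somewhat lower, by c_int × (12 − m)/12. The credited version stays available for readers interested in appropriate care.
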